The expected	The screening period from signing the informed consent form to enrollment is expected to be 4 weeks, the treatment period is 1~8 weeks, and the short-term follow up after the last treatment are divided into
the	short-term follow-up and long-term follow-up, and the maximum duration
unc narticinant's	of expected participation of each subject from screening to the end of short-term
participation	follow-up is 12 weeks +3 months. Long-term follow-up continued after the end of the
participation	short-term follow-up until the fifth year after the end of the last radiotherapy.
Expected	The first subject is expected to be enrolled in December 2021, and the clinical trial
overall	institution expects to enroll 8-18 subjects per month, for a total enrollment time of
duration of	about 4 months, and the last 1 subject ends the trial (short-term follow-up) is End In
clinical trials	September 2022, the overall duration of the clinical trial included all working
and long-term	hours before, during and after the start of all clinical trials, and the overall duration of
follow-up	the clinical trial was 16 months.

Protocol summary

	The first subject is expected to start long-term follow-up in May 2022 and the last		
	one subject to end long-term follow-up in June 2027, and the overall duration		
	of long-term follow-up in clinical trials includes all clinical runs, After all working		
	hours ended, the total long-term follow-up period for clinical studies was		
	approximately 62 months.		
	Disease Control Rate (DCR).		
	Evaluation time: 3 months ± 7 days after the last treatment.		
	Definition of indicators: Complete Response (CR), Partial Response (PR), Stable		
	Disease (SD) for disease control; No biochemical recurrence at the end of prostate		
D .	cancer treatment, no regional lymph nodes or distant metastases, considered disease		
Primary	control. Proportion of participants who developed disease control three months after		
effectiveness	the end of the last radiotherapy. Participants who discontinued the trial for any reason		
Evaluation	(except loss to follow-up) before the end of radiation therapy were considered to have		
indicators	progression (PD) or uncontrolled.		
	Evaluation methodology: Response Evaluation Criteria in Solid Tumors RECIST		
	Version 1.1 (RECIST 1.1) by an independent imaging review team Changes in		
	tumour CT or MRI imaging before and after treatment were assessed. At 3 months		

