3.1.4 Effectiveness evaluation methods

If it is not possible to follow up at the clinical trial center according to the visit arrangement due to the epidemic, the clinical examination can be examined by other tertiary hospitals, and the test results will be transmitted back to the clinical trial center for evaluation; The carrier of imaging data in the outer hospital is not limited, and it is necessary to ensure that the imaging department of the center can be opened and read.

3.1.4.1 The main effectiveness evaluation indicators and the methods and time selection of their evaluation, recording and analysis

(1) Tumor disease control rate (DCR).

Reason for selection: According to the clinical trial effectiveness evaluation in the "Guidelines for the Review of Clinical Evaluation Technologies of Proton Carbon Ion Therapy System" (CFDA Circular No. 4 [2018]): "In view of the local characteristics of radiotherapy, it is recommended that the efficacy evaluation should be based on local control, and according to the different diseases, the common standards in clinical research, such as the efficacy evaluation criteria for solid tumors, should be reasonably adopted RECIST. The efficacy evaluation can be divided into complete response CR, partial response PR, disease stable SD, disease progression PD, and the effective definition is: "CR+PR+SD." "; Due to the particularity of the disease, the evaluation method recommended in the relevant diagnosis and treatment guidelines is selected. The tumor disease

control rate was selected as the main effectiveness evaluation index, which was relatively objective and reproducible, and adopted the common standard in clinical research, which was widely recognized and applied by clinicians.

Definition of indicators: the occurrence of CR, PR and SD after the end of treatment is disease control; No biochemical recurrence at the end of prostate cancer treatment, no regional lymph nodes or distant metastases, considered disease control. Proportion of participants who developed disease control three months after the end of the last radiotherapy.

Metric type: Qualitative.

Data collection time: screening period, 3 months \pm 7 days after the end of the last treatment.

Evaluation time: 3 months \pm 7 days after the end of the last treatment.

Site of evaluation: Tumor receiving radiation therapy.

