Evaluation method: The changes in tumor CT or MRI imaging before and after treatment were evaluated by an independent imaging review panel according to RECIST 1.1. At 3 months of radiographic evaluation, if PD is found, PET-CT is required to confirm it.

Calculation formula: DCR = number of disease control subjects / total number of subjects × 100%.

Criteria: See RECIST 1.1 for details. At the time of 3-month imaging evaluation, if the patient is found to have PD, PET-CT examination is required to confirm it, if progress is confirmed, it is recorded as PD, if progress cannot be confirmed, it may be false progression, and it is recorded as SD. If prostate cancer does not have biochemical recurrence, PET-CT examination is not required, and there is no metastasis by default, which is regarded as tumor control, and if biochemical recurrence occurs, it is regarded as tumor not controlled, and PET-CT is required to confirm tumor metastasis.

Note: Participants who aborted the trial for any reason (except loss to follow-up) before the end of the last radiation therapy were considered to have disease progression (PD) or were not controlled. Disease site evaluation uses the same approach as baseline, including consistent contrasted/non-contrast scans and prompt scanning. If changes are needed, the case must be discussed with a radiologist to determine whether an alternative approach is possible. If not, the objective situation in the future is unclear.

3.1.4.2 Secondary effectiveness evaluation indicators and their methods and timing of evaluation, recording, analysis

(1) Objective response rate (ORR).

Reason for selection: The Guidelines for the Review of Clinical Evaluation Technologies of Proton Carbon Ion Therapy Systems (CFDA Circular No. 4 [2018]) recommends the use of the latest version of the commonly used evaluation criteria for radiation oncology as the clinical trial evaluation criteria, so RECIST 1.1 is used Relevant indicators as effectiveness evaluation criteria; Due to the particularity of the disease, the evaluation method recommended in the relevant diagnosis and treatment guidelines is selected. All of them can directly measure the effect of radiotherapy and are widely recognized and applied by clinicians.

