Reason for selection: The Guidelines for the Review of Clinical Evaluation Technologies of Proton Carbon Ion Therapy Systems (CFDA Circular No. 4 [2018]) recommends the use of the latest version of the commonly used evaluation criteria for radiation oncology as the clinical trial evaluation criteria, so RECIST 1.1 is used Relevant indicators as effectiveness evaluation criteria; Due to the particularity of the disease, the evaluation method recommended in the relevant diagnosis and treatment

guidelines is selected. They are all commonly used indicators for the evaluation of tumor treatment effects, and are widely recognized and applied by clinicians.

Indicator definition: the time between the first assessment of the tumour as CR or PR and the time between the first assessment of PD or death from any cause.

Indicator type: quantitative.

Data collection time: 1 month \pm 7 days, 3 months, \pm 7 days after the end of the screening period, until tumor progression or subject death.

Evaluation time: 3 months \pm 7 days after the last treatment.

Site of evaluation: Tumor receiving radiation therapy.

Evaluation method: The changes in tumor CT or MRI imaging before and after treatment were evaluated by an independent imaging review panel according to RECIST 1.1. At 3 months of radiographic evaluation, if PD is found, PET-CT is required to confirm it.

Calculation formula: DOR = time to death from PD or any cause on the first assessment - time to CR or PR for the first assessment;

Criteria: See RECIST 1.1 for details. At the time of 3-month imaging evaluation, if the patient is found to have PD, PET-CT examination is required to confirm it, if progress is confirmed, it is recorded as PD, if progress cannot be confirmed, it may be false progression, and it is recorded as SD.

Note: If no tumor progression or death is observed during the follow-up period after the end of radiotherapy, the formula is: DOR > last visit time after the end of the last radiotherapy - CR or PR time for first assessment. Others are the same as ORR.

(3) Tumor disease control rate (DCR).

Reason for selection: DCR 3 months after the end of the last treatment was the primary evaluation index, and DCR at other follow-up time was used as a secondary evaluation index.

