4.3 Effectiveness indicators are missing

When analysing the main effectiveness evaluation indicators based on PPS, it is not necessary to consider filling them.

In the sensitivity analysis of the main effectiveness evaluation indicators based on FAS, the missing values of the main effectiveness evaluation indicators were not filled.

The missing values of qualitative secondary effectiveness evaluation indicators ORR and DCR were filled by the method of worst observational data carryover (WOCF).

The missing value of the quantitative secondary effectiveness evaluation index DOR was not filled.

Other secondary effectiveness evaluation indicators, such as tumor markers, tumor-specific symptoms, and

Confidential Information Page 9 / 17

rsion: V1.0 Date: 2022-11-11

product ease of use, were not filled.

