5.4 Effectiveness evaluation indicators

5.4.1 Key Effectiveness Indicators

The primary effectiveness evaluation was based on the Full Analysis Set (FAS) and the Protocol-Consistent

Set (PPS).

The number and percentage of cases that achieved tumor disease control at 3 months during the follow-up

period were calculated, and the 95% confidence interval of tumor disease control rate was calculated by Clopper-

Pearson, and the target value of tumor local control rate was 80%, and if the lower limit of the 95% confidence

interval of the test results was greater than 80%, the tumor local control rate was reached. The single-sample chi-

square test was used to compare whether there was a statistical difference between the local control rate and the

target value.

For the evaluation results of the imaging review team, if the efficacy evaluation results of the two evaluators

are consistent, the final evaluation results of the two evaluators will be taken, and if the evaluation results of the

two evaluations are inconsistent, the independent evaluation value of the third evaluator will be taken as the final

evaluation results.

Based on FAS, the sensitivity analysis of the main effectiveness indicators was carried out, and the missing

values of the main effectiveness evaluation indicators were filled by the method of Worst Observational Data

Confidential Information Page 12 / 17

Statistical Analysis Plan Version: V1.0
Date: 2022-11-11

Carryover (WOCF).

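### Deaths and withdrawals between the end of radiotherapy and the month-3 assessment have no single scoring rule, and the SAP can drop them from the deciding DCR result or score them as controlled

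*Protocol*

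**What the plan says.** - **Endpoint.** Protocol 3.1.4.1 defines DCR as "Proportion of participants who developed disease control three months after the end of the last radiotherapy", with a window of ± 7 days, and computes it as "DCR = number of disease control subjects / total number of subjects × 100" percent. The formula is not tied to an analysis set.
- **Early exit.** Protocol 3.1.4.1 (Note): "Participants who aborted the trial for any reason (except loss to follow-up) before the end of the last radiation therapy were considered" to have PD or to be uncontrolled. The synopsis has the same cut-off and the same exemption for loss to follow-up. SAP 2.1.1 does not carry the rule.
- **PD at the month-3 scan.** It goes to PET-CT: "if progress is confirmed, it is recorded as PD, if progress cannot be confirmed, it may be false progression, and it is recorded as SD".
- **Missing month-3 values.** Protocol 4.7.2 item (3) allows, but does not require, a worst-case estimate. SAP 4.3 says "When analysing the main effectiveness evaluation indicators based on PPS, it is not necessary to consider filling them", and also leaves the FAS sensitivity analysis unfilled. SAP 5.4.1 says of that same FAS analysis that missing "values of the main effectiveness evaluation indicators were filled by the method of Worst Observational Data" carryover. SAP 5.6 also links the FAS analysis to WOCF, and SAP 4.1 lets WOCF use unscheduled data.
- **Which set decides.** The PPS is the main efficacy population (Protocol 4.9, SAP 3) and takes precedence if it disagrees with the FAS (SAP 5.6).
- **Declared changes.** SAP section 6 lists only the conventions for missing AE severity and relatedness.

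**The concern.** Radiotherapy lasts 1 to 8 weeks. The endpoint is read three months later, and the plan's own failure rule is silent over that interval. People who die or leave in those months are likely to include some of the failures that the endpoint is meant to count.

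Take a subject with SD at month 1 who dies at week 8 after radiotherapy. No month-3 category exists. In the PPS nothing is filled, so the subject can vanish from the result. If the FAS is filled by WOCF and nothing worse than SD was recorded, the death is carried into the analysis as disease control. A subject with PD at month 1 who leaves before month 3 can also go unscored in the PPS. Elsewhere the protocol does treat death as an event: duration of response ends at "the time between the first assessment of PD or death from any cause".

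This is a single-arm registration trial judged against a fixed target, so any such loss of failures moves the result toward success.

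**Working it through.** **1. The plan's own figures.** Inputs: target 80% (Protocol 4.2), expected value 95% (Protocol 3.1.2), two-sided α 0.05 and power 80% (Protocol 4.3), dropout 10% (Protocol 4.4).

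n = [(1.960·√(0.8·0.2) + 0.842·√(0.95·0.05)) / 0.15]² = 41.6, rounded up to 42. Then 42/0.9 = 46.7, rounded up to 47. Both figures reproduce.

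**2. How many failures the success rule allows.** Success needs a two-sided 95% Clopper-Pearson lower limit above 80% (Protocol 4.5, SAP 5.4.1). The smallest passing counts are 38/41 (80.1%), 39/42 (80.5%), 40/43 (80.9%), 41/44 (81.3%), 42/45 (81.7%), 43/46 (82.1%) and 44/47 (82.5%). That is at most 3 failures at every N from 41 to 47.

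**3. One post-radiotherapy exit among 4 failures.**
- Counted in the PPS: 38/42, lower limit 77.4%, fails.
- Left out of the PPS: 38/41, lower limit 80.1%, passes.
- The same reversal at the top of the range, if all 47 would otherwise be in the set: 43/47, 79.6%, fails; 43/46, 82.1%, passes.
- FAS sensitivity analysis, all 47: 43/47, 79.6%, fails; if WOCF turns one death into SD, 44/47, 82.5%, passes.

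**4. Chance of false success.** The documents give no rate q of post-radiotherapy exit, so the values below are assumptions. Let the true rate be exactly 80% with exits counted as failures, so control among those assessed is 0.80/(1 − q). With exits left out of 47 subjects,

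P(success) = Σₘ Bin(m; 47, q) · P[Bin(47 − m, 0.80/(1 − q)) ≥ r(47 − m)],

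where r(n) is the smallest passing count.

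| q | exits left out | exits counted |
|---|---|---|
| 0% | 0.9% | 0.9% |
| 2% | 2.1% | 0.9% |
| 5% | 6.3% | 0.9% |
| 10% | 26.2% | 0.9% |

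The nominal one-sided level of a two-sided 95% interval is 2.5%.

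**5. The sections side by side.** For the same missing month-3 value, Protocol 4.7.2(3) permits not controlled, SAP 4.3 leaves it empty in both sets, and SAP 5.4.1 with 5.6 carries forward the worst earlier category in the FAS. SAP 4.3 and 5.4.1 contradict each other. The move away from worst case is not declared in SAP section 6.

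**The case against.** The other side has real points.

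- **The interval is not wholly without a rule.** Protocol 4.7.2(3) allows worst case for a missing month-3 DCR, which would score these subjects as not controlled. That stands, but the wording is permissive and the SAP does not apply it.
- **Progression is mostly caught.** A reader might infer that anyone who progresses after radiotherapy escapes the count. The documents do not support that: PD seen at month 3 counts once PET-CT confirms it, and WOCF would carry earlier PD forward, including from unscheduled data. Only a progressor with no month-3 assessment is exposed.
- **Exclusion from the PPS is one reading.** Taken literally, dividing by all subjects keeps an unfilled subject in the denominator, which gives 38/42. It is also unclear whether a month-1 scan, a secondary measure, qualifies a subject for the PPS. Against this, Protocol 4.4 lists missing key data as a reason for not entering the primary analysis, which favours exclusion. The text leaves both readings open.
- **A death may fail the trial anyway.** Any grade 4 or 5 toxicity is a trial failure (Protocol 4.5), and SAP 5.5.1 describes grade 5 as AE-related death. A death recorded that way may decide the trial on safety. This does not correct the DCR and does not reach withdrawals.
- **Counting every death as loss of control is a choice of estimand.** The endpoint concerns the irradiated tumour, and a time-to-event measure such as duration of response needs a death rule in a way that a rate does not. This is fair. It is a reason to state the choice, not to leave it open.

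**Conclusion.** The point holds as a gap and an inconsistency. The failure rule stops at the end of radiotherapy, the SAP endpoint definition omits it, and the later sections give three different treatments of the same missing value. Following the SAP, a death or withdrawal before month 3 can drop out of the deciding PPS result. In the FAS, WOCF can score a later death as controlled, provided that nothing worse than SD was recorded.

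One subject is enough to change the PPS result (38/42 against 38/41). That example assumes 4 failures, one of them a post-radiotherapy exit, and that an unfilled subject leaves the denominator.

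Two stronger readings go too far. A reader might infer that the primary DCR is biased upward as a matter of fact. The documents give no exit rates, so the bias is conditional on such exits occurring and being left out. A reader might also take the 47-subject WOCF example as changing the trial's verdict. It concerns only the FAS sensitivity analysis, and SAP 5.6 gives precedence to the PPS.

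**What to change.** 1. In Protocol 3.1.4.1 (and the synopsis) and SAP 2.1.1, extend the existing rule: *death, or leaving the trial for any reason other than loss to follow-up, at any time before the month-3 assessment is counted as not controlled. Earlier PD with no month-3 assessment is also counted as not controlled. Earlier PD that is assessed again at month 3 follows the existing PET-CT confirmation rule.* The last sentence keeps unconfirmed progression scored as SD.
2. State that this outcome is assigned in both PPS and FAS before any filling, that it counts as a primary assessment for PPS membership, and that these subjects stay in the denominator.
3. Reconcile SAP 4.3 and 5.4.1 (with 5.6) with Protocol 4.7.2(3): use worst case, not WOCF, for month-3 values still missing in the FAS. List any remaining departure in SAP section 6.
4. Add a sensitivity analysis that shows deaths unrelated to the tumour separately.

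The cost is wording. Withdrawals and their reasons, AEs and month-1 imaging are already collected. It should be settled before database lock, because Protocol 4.8 treats later additions as exploratory.

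The downside is that reported DCR may be somewhat lower and unrelated deaths count as not controlled. Power also falls if the expected 95% refers only to subjects who are scanned, which the documents do not say. With 47 subjects and that assumption, power is 59.1% rather than 80.2% at 2% exits, and 31.5% rather than 81.5% at 5%. The sponsor should state what the 95% covers.

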3.1.2 Choice of trial method and justification

This trial was designed using the prospective, two-center, single-group target value method.

- (1) Prospective study: Adopt a research approach that traces from the present to the future. Prospective studies can establish cause and effect; There are unified diagnosis, detection and evaluation standards for the obtained data, so the data processing is controllable.
- (2) Two centers: Select 2 clinical trial institutions to carry out the clinical trial. More cases than single-center trials can be obtained in the same amount of time, thus shortening the duration of clinical trials.
- (3) Single-group target value method: Because the same device of the experimental medical device is radioactive and difficult to obtain, the existing treatment method is not feasible due to objective conditions, so the single-group target value method is adopted. Moreover, the applicable population and main evaluation indicators of experimental medical devices can be fully defined and relatively stable; The main evaluation index adopts the effective rate mentioned in the "Guidelines for the Technical Review of Clinical Evaluation of Proton Carbon Ion Therapy System" (CFDA Circular No. 4 [2018]), which is relatively objective and reproducible. According to the Guidelines for the Technical Review of Clinical Evaluation of Proton Carbon Ion Therapeutic response rate for experimental medical devices should be at least 80%, and the expected value should be 95%. Among them, the effective definition is: CR+PR+SD (complete response CR, partial response PR, disease stable SD), which is basically consistent with the definition of tumor disease control rate in this clinical trial. Therefore, no control group was set up in this clinical trial, and the single-group target value method was used to evaluate whether the tumor disease control rate reached the target value (80%) and the main safety evaluation index CTCAE 3 when ProBeam was used in

radiotherapy for tumor patients Whether the proportion of grade toxicities is less than acceptable (5%) and whether the proportion of CTCAE grade 4 and 5 toxicities is acceptable (0%).

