4.2 Sample size calculation

4.2.1 Total sample size

This clinical trial intends to enroll 47 subjects. The sample size determination process is as follows:

This clinical study is designed for clinical verification of a single group of target values, and the tumor disease control rate, the main effectiveness evaluation index, is used as the basis for sample size estimation. According to the Guidelines for the Review of Clinical Evaluation Technologies of Proton Carbon Ion Therapy System (CFDA Circular No. 4 of 2018), the target value is set at 80%, and the bilateral significance level is 0.05, and the power degree 80%, applying the sample size estimation professional software PASS 15.0, calculated by the above parameters, the test group needs a sample size of at least 42 cases. Considering that about 10% of cases may be dropped or lost to follow-up during clinical validation, the sample size of the experimental group was expanded to 47 cases.

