4.3 The level of significance and power of clinical trials

The significance level α (bilateral) = 0.05, and the power was 80%.

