4.4 Expected shedding rate

In the sample size estimation process, the expected shedding rate is 10%.

This dropout rate refers to the proportion of participants who ultimately could not be included in the primary analysis. Shedding subjects are subjects who have been identified by the investigator as having serious protocol deviations. May include, but is not limited to, the following: the subject violates the inclusion criteria; Participants were not treated with experimental devices; Participants used concomitant medications/devices that are prohibited by the protocol; lack of data on key evaluation indicators; Participants did not obtain any data, etc.

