2.1 Effectiveness evaluation indicators

2.1.1 Key Effectiveness Indicators

• Tumor disease control rate (DCR) at 3 months after the end of last treatment

The occurrence of CR, PR and SD after the end of treatment was considered to be disease control, and the

absence of biochemical recurrence at the end of treatment of prostate cancer was considered to be disease control.

Proportion of subjects with disease control 3 months after the end of the last radiation therapy.

Calculation formula: DCR = number of subjects under disease control / total number of subjects \times 100%

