5.3.8 Concomitant therapy

A detailed description of the subject's concomitant treatment based on the FAS list.

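### No rule scores a subject whose irradiated tumour progresses after the last fraction, who then gets other unplanned anticancer treatment, and whose month-3 scan shows control

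*Protocol*

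**What the plan says.** Protocol 3.1.4.1 defines DCR from CR, PR or SD of the irradiated tumour at 3 months ± 7 days, with imaging at screening and month 3 as the only data collected for it. PD on that scan needs PET-CT confirmation. For prostate cancer, control rests on absence of biochemical recurrence. SAP 2.1.1 gives the same single-time definition: "Proportion of subjects with disease control 3 months after the end of the last radiation therapy".

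The note in protocol 3.1.4.1 adds the one event-based rule: subjects who "aborted the trial for any reason (except loss to follow-up) before the end of the last radiation therapy were considered to have disease progression" or uncontrolled. It ends with the last fraction.

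Other treatment appears in two places. Protocol 4.4 lists among serious deviations that take a subject out of the primary analysis: "Participants used concomitant medications/devices that are prohibited by the protocol". SAP 5.3.8 provides a listing only: "A detailed description of the subject's concomitant treatment based on the FAS list". SAP 5.3.7 tabulates medications. Neither SAP section links these data to DCR or ORR.

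The PPS (protocol 4.9, SAP 3) needs measurable baseline disease and one post-baseline primary efficacy assessment. It does not mention other anticancer treatment. SAP 5.3.2 leaves exclusions to a data review meeting and gives no criterion for this case. SAP 5.6 lets the PPS result prevail if FAS and PPS disagree.

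**The concern.** Take a subject whose irradiated tumour has progressed at month 1, who starts unplanned treatment for it, stays in the trial and shows SD or better against baseline at month 3. ProBeam did not control this tumour, but the written definition counts the subject as controlled, and as an objective responder if the scan is CR or PR. The worst-case and WOCF rules (protocol 4.7.2, SAP 5.4.1 and 5.6) act on missing values, and here nothing is missing. Protocol 4.4 might remove the subject, but removal is not failure, and the PPS definition does not carry that exclusion. The same subject can therefore be a success under one section and absent under another.

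The objective is to show for registration that ProBeam radiotherapy reaches a fixed 80% target. With no control arm, any effect of the other treatment on the month-3 scan is credited to the device. The case is foreseeable: the trial takes many tumour sites, and the month-1 review for secondary DCR and ORR can show progression two months before the primary assessment.

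**Working it through.** **Inputs.** Target 80% and two-sided alpha 0.05 (protocol 4.2.1: "the target value is set at 80%, and the bilateral significance level is 0.05"); power 80% (4.3); expected rate 95% (3.1.2: "should be at least 80%, and the expected value should be 95", in per cent); evaluable n (4.2.1: "the test group needs a sample size of at least 42 cases"); 10% dropout; pass if the Clopper-Pearson 95% lower limit exceeds 80% (4.5, 4.7.1).

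**Step 1: the plan's own figures.**
n = [(1.960·√(0.80·0.20) + 0.842·√(0.95·0.05)) / 0.15]² = 41.6, so 42. Then 42/0.90 = 46.7, so 47. Both reproduce.

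**Step 2: the pass threshold.** The Clopper-Pearson lower limit for x of n is the 2.5% quantile of Beta(x, n−x+1).

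| Result | Lower limit | Pass? |
|---|---|---|
| 39/42 | 80.5% | yes |
| 38/42 | 77.4% | no |
| 44/47 | 82.5% | yes |
| 43/47 | 79.6% | no |

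Three failures are tolerated at either size. At the threshold, one subject moved from controlled to not controlled reverses the verdict.

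**Step 3: exclusion instead of failure.** At 43/47 the trial fails. Dropping one of the four failures gives 43/46, lower limit 82.1%, which passes. Dropping a subject who would have counted as controlled works the other way: 38/41 passes (80.1%), while 37/40 fails (79.6%).

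**Step 4: scenarios.** The documents give no rate of other treatment, so the rescued share r is an assumption. With true device-only control p, the recorded rate is p + (1−p)·r, and the chance of passing is P(X ≥ 39) for n=42 or P(X ≥ 44) for n=47.

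With p = 80%:

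| r (assumed) | Recorded rate | Pass, n=42 | Pass, n=47 |
|---|---|---|---|
| 0 | 80% | 2.1% | 0.9% |
| 5% | 81% | 3.0% | 1.4% |
| 10% | 82% | 4.2% | 2.1% |
| 25% | 85% | 10.7% | 6.4% |
| 50% | 90% | 38.4% | 29.6% |

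With p = 95% and r = 25%, the recorded rate is 0.95 + 0.05·0.25 = 96.25%. The chance of passing goes from 84.3% to 92.8% (n=42) and from 79.3% to 90.1% (n=47).

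**The case against.** Several points on the other side stand and set the limits of this one.

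- A reader might infer that leaving before the end of radiotherapy is the only way to fail. It is not. Confirmed PD and biochemical recurrence are failures, and protocol 4.7.2 allows worst-case scoring of a missing month-3 result. A subject who progresses, leaves and has no month-3 result comes under protocol 4.7.2 and SAP 4.3 and 5.4.1. Those sections disagree on filling, but that is a separate matter.
- A reader might count residual tumour at month 1 as a device failure. Under the endpoint definition SD and PR are control, so only progression of the irradiated tumour qualifies.
- A reader might conclude that the gap always favours passing. Step 3 shows that excluding a controlled subject can do the reverse.
- High rescue rates have no support in the documents. Progression first seen at month 3 cannot be rescued before it. At 5% to 10% the effect is small in absolute terms.
- Scoring the month-3 scan regardless of other treatment is a legitimate choice if it is stated and accompanied by a sensitivity analysis.
- Rules on prohibited treatment may lie outside the supplied text: SAP 6 cites a protocol section 8.7.2 for what is numbered 4.7.2 here. Under protocol 4.4, however, use of prohibited treatment leads to exclusion, not failure.

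None of this says how to score the subject who stays in and has a controlled scan.

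**Conclusion.** The point holds in a limited form. For a subject with an available month-3 scan, only aborting before the last fraction overrides it. A subject with progression of the irradiated tumour, other unplanned treatment and a controlled month-3 scan can count as a success under the FAS and PPS definitions, or be left out under protocol 4.4. Neither outcome is a failure, and the sections need to be reconciled.

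That one subject can decide the trial follows from the plan's own rule and needs no assumption about rates. The pass probabilities are scenarios. They rest on an assumed rescued share, on independent subjects, and on 42 or 47 analysed. The documents do not support a claim that rescue is common or that the result will be biased by a particular amount. The point merits a change because the remedy is cheap and no comparator offsets the effect.

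**What to change.** In protocol 3.1.4.1 and SAP 2.1.1 and 5.4.1, add a scoring rule for the primary analysis:

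- **Trigger.** Between first treatment and the month-3 assessment, the subject starts unplanned anticancer treatment that is directed at the irradiated tumour, or that is systemic and given for its progression.
- **Score.** Not controlled at month 3, and non-responder for month-3 ORR.
- **Not a trigger.** Treatment only for disease outside the irradiated tumour, and adjuvant or concurrent therapy planned and documented before first treatment.
- **Classification.** Each case is decided before database lock without sight of the month-3 result.
- **Analysis sets.** These subjects stay in FAS and PPS. Amend protocol 4.4 so that such treatment is not a reason for removal from the primary analysis.
- **Sensitivity analysis.** Report DCR regardless of such treatment.

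Costs: DCR may be slightly lower. A subject with SD or PR who gets further treatment of the irradiated tumour counts as a failure, which is conservative. Planned therapy must be documented before first treatment, which the supplied text does not show is done. Timing can use the start-date rules already in SAP 4.2. The change concerns endpoint scoring only, not which treatments patients may receive.
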